14.2.5 Secondary Objectives

14.2.5.1 Change in IOP and Number of Topical IOP-Lowering Medications 4 Years after XEN 45 Gel Stent Implantation

Change in IOP from medicated baseline and change in the number of topical IOP-lowering medications compared to baseline will be summarized descriptively at Year 4 after XEN 45 Gel Stent implantation in eyes from the Analysis Population with at least 4 years of follow-up data and were not treated with Diamox on the day when decision was taken to implant XEN 45 Gel Stent.

14.2.5.2 Success over the Long Term of following implantation of the XEN 45 Gel Stent

Number and proportion of eyes achieving a 20% reduction in IOP from medicated baseline, and number and proportion of eyes with an IOP <18 mmHg, IOP <17 mmHg, ..., down to IOP <12 mmHg will be described at all time-points of interest in eyes from the Analysis Population that did not undergo SSI for glaucoma, did not have clinical hypotony, and were not treated with Diamox on the day when decision was taken to implant XEN 45 Gel Stent.

The number and proportion of eyes achieving qualified or complete success at 3 and 4 years after XEN 45 Gel Stent implantation will be summarized descriptively. Analyses will be conducted in the Analysis Population. Kaplan-Meier analyses will be conducted to analyze time from initial procedure to SSI for glaucoma.

14.2.5.3 Safety over the long term following implantation of the XEN 45 Gel Stent

Surgical complications and post-operative AESIs will be summarized descriptively using frequencies and percentages. Analyses will be performed in the Analysis Population.

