1.4. Key Variable Definitions

Qualified success of implantation of the XEN 45 Gel Stent will be defined as $\geq 20\%$ reduction from medicated baseline with no Secondary Surgical Intervention (SSI) for glaucoma and no clinical hypotony while staying on the same number or fewer topical IOP-lowering medications than at baseline.

Complete success of implantation of the XEN 45 Gel Stent will be defined as $\geq 20\%$ reduction from medicated baseline with no SSI for glaucoma and no clinical hypotony while taking no topical IOP-lowering medications.

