3.4. Missing Data

The eCRF is designed to ensure that no questions are left unanswered. If 'unknown' is selected, this will be included as such in the results and tabulated for all variables. Central tendencies will not be measured for continuous unknown data, only counts and percentages will be recorded.

In some cases, imputation of unknown variables may be conducted if the variable is to be used in calculations for another variable or analysis. For example, the eCRF allows some dates to be incomplete (i.e. day is unknown) if it is not available in the medical chart. This may impact accurate calculation of durations, resulting in an imputation needing to be made. If the day is missing, the date will be imputed as the 15th of the month, except in cases where this would lead to a negative duration, in which case the 1st or last day of the month will be used (whichever addresses the negative duration). No imputation will be made for missing month/year; these are classified as date unknown within the eCRF. All imputed values will be documented and presented as footnotes in the result tables.

4. Planned Analyses

The analyses detailed below will be performed to meet the project objectives. There will be two analysis populations specified for the analyses to be conducted:

- The **Effectiveness Population** consists of all eligible study eyes in the population except in instances when a patient has contributed both eligible eyes in the study, then only the eye that received the Xen-45 implant first will be selected; this eye will be presented in tables as the 'primary eye'. All results tables in the Effectiveness Population will include stratified results presenting data for the primary eye, as well as data on all included patient eyes (even if both eyes from a single patient are included).
- The **Safety Population** consists of all eligible study eyes in the population.

All results tables will be stratified by Xen-45 implant only, implant plus phacoemulsification, and total population. Sensitivity analyses will be conducted to assess study results in the 'second eye' (i.e. not the primary eye as described above), for patients where both eyes were included. The sensitivity analyses will focus on the tables conducted using the Effectiveness Population.

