These will be compared to baseline and will be summarised descriptively at months 12, 24, 36 and 48 after XEN 45 Gel Stent implantation in eyes from the Effectiveness Population. Analyses will only include those with available data at each of the time points of interest and those who were not treated with Diamox on the day when decision was taken to implant XEN 45 Gel Stent.

A paired t-test will be applied for statistical analysis in comparing the difference between post baseline to baseline values. The assumptions of the test are as follows:

- No significant outliers in the differences between time points (which can be tested by a scatter plot of the data)
- The distribution of the differences in the dependent variable between the two time points should approximately follow a normal distribution (which can be tested through the Shapiro-Wilk test)
- The dependent variable is measured on a continuous scale

If the assumptions of the t-test are heavily violated then the non-parametric analogue (Wilcoxon Signed-Rank test) should be used to test the difference between time points.

4.4.1. Success over the long term of following implantation of the XEN 45 Gel Stent

Number and proportion of eyes achieving a 20% reduction in IOP from medicated baseline, and number and proportion of eyes with an IOP between 6 and 18 mmHg, IOP between 6 and 17 mmHg, ..., down to IOP between 6 and 12 mmHg will be described by the time-windows described in Section 4.1 in eyes from the Effectiveness Population that did not undergo SSI for glaucoma, and were not treated with Diamox on the day when decision was taken to implant XEN 45 Gel Stent.

The number and proportion of eyes achieving qualified or complete success at each time point of interest (i.e. 12, 24, 36, 48 and >51 months) after XEN 45 Gel Stent implantation will be summarised descriptively. Analyses will be conducted in the Effectiveness Population.

The time from XEN 45 Gel Stent implantation to SSI for glaucoma will be described using Kaplan Meier curves.

4.5. Safety over the long term following implantation of the XEN 45 Gel Stent

Surgical complications and post-operative AESIs will be summarised descriptively using frequencies and percentages.

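### Qualified and complete success are scored with baseline-Diamox eyes included, while the IOP-change, 20%-reduction and threshold results exclude them, with no reason given and no supportive row

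*SAP*

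**What the plan says.** **IOP and medication change.** SAP 4.4 limits these summaries: "Analyses will only include those with available data at each of the time points of interest and those who were not treated with Diamox". The Diamox status meant is that of the decision day. Protocol 14.2.4 (Year 3) and 14.2.5.1 (Year 4) apply the same Diamox exclusion.

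**20% reduction and IOP thresholds.** The first paragraph of SAP 4.4.1 uses Effectiveness Population eyes that had no secondary surgical intervention (SSI) for glaucoma and "were not treated with Diamox on the day when decision was taken to implant XEN 45 Gel Stent". Protocol 14.2.5.2 applies the same two restrictions and also drops eyes with clinical hypotony.

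**Qualified and complete success.** The second paragraph of SAP 4.4.1 reports "The number and proportion of eyes achieving qualified or complete success at each time point of interest". Its only statement on the analysis set is this: "Analyses will be conducted in the Effectiveness Population". Protocol 14.2.5.2 says of success: "Analyses will be conducted in the Analysis Population". Neither sentence mentions Diamox.

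**Definitions.** SAP section 4 defines the Effectiveness Population as a set that "consists of all eligible study eyes in the population except in instances when a patient has contributed both eligible eyes in the study"; for such patients the first-implanted eye is taken. Diamox plays no part. Under SAP 1.4, both forms of success require a reduction of at least 20% from medicated baseline, no SSI and no clinical hypotony. Qualified success adds "while staying on the same number or fewer topical IOP-lowering medications than at baseline"; complete success requires no topical drug at all.

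**The concern.** The 20% responder result and qualified success share their central criterion and their baseline. In the outcome lists (Protocol 6.3, SAP 1.5) they are closer still, because the 20% outcome there also requires no increase in topical drugs and no clinical hypotony. A reader will set the two tables side by side. One includes eyes that were on Diamox when baseline IOP was recorded and the other does not.

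The medication component of success does not bridge this gap. It counts topical drugs, so if Diamox is the oral drug that its separate handling suggests, starting or stopping it does not register there.

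At stake is the reading of a secondary, descriptive result. As planned, no success rate will be available on the Diamox rule that governs the IOP-change and 20% results.

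**Working it through.** **1. Analysis sets side by side (SAP)**

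| Result | Uses baseline IOP? | Baseline-Diamox eyes | SSI eyes |
|---|---|---|---|
| Change in IOP (4.4) | Yes | Excluded | No separate rule; data needed at the visit |
| 20% reduction (4.4.1, first paragraph) | Yes | Excluded | Excluded |
| IOP thresholds (4.4.1, first paragraph) | No | Excluded | Excluded |
| Qualified and complete success (4.4.1, second paragraph) | Yes | No exclusion stated | Failures by definition (1.4) |

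Dependence on baseline IOP does not explain the pattern. The threshold results do not use it yet drop the Diamox eyes; success uses it and keeps them.

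**2. Do the Diamox eyes drop out earlier?** No. The Protocol 8.2.1 and SAP 1.7 criteria do not mention Diamox, Protocol 8.2.2 has no exclusion criteria, and neither population definition mentions it.

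**3. Is there a supportive analysis?** The sensitivity analyses in SAP section 4 concern the second eye of bilateral patients. None concerns Diamox.

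**4. The plan's own figures.** The documents give no planning figure for success and no number of Diamox eyes. The one computable planning figure reproduces: 1.96 × 6.32 / √60 = 1.60, so -5.6 ± 1.6 gives -7.2 to -4.0 mmHg. It concerns mean IOP change and is not affected by this point.

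**5. Possible size (all inputs assumed).** Let d be the share of Diamox eyes, p0 the success rate in the other eyes and pD the rate in Diamox eyes. Then

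success in all eyes = (1 - d) × p0 + d × pD, and the shift against the non-Diamox rate = d × (pD - p0).

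With p0 = 50%:

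| d | pD = 10% | pD = 30% | pD = 50% | pD = 70% |
|---|---|---|---|---|
| 2% | -0.8 | -0.4 | 0 | +0.4 |
| 5% | -2.0 | -1.0 | 0 | +1.0 |
| 10% | -4.0 | -2.0 | 0 | +2.0 |
| 20% | -8.0 | -4.0 | 0 | +4.0 |

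Shifts are in percentage points. The extremes are 0.20 × (0.10 - 0.50) = -0.08 and 0.20 × (0.70 - 0.50) = +0.04. For scale, a 50% proportion in 60 eyes has a 95% half-width of 1.96 × √(0.5 × 0.5 / 60) = 0.127, or 12.7 points.

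**6. The other difference.** Suppose 50% of eyes without SSI meet the criteria, and a share s of all eyes had SSI and count as failures. Success is then 0.50 × (1 - s): 47.5% at s = 5%, 45% at 10% and 40% at 20% (s is also assumed). This gap would exist with no Diamox eyes in the study.

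**The case against.** **The sets differ by design anyway.** This stands. SSI eyes, and in the protocol clinical-hypotony eyes, leave the 20% table's denominator but are failures in success. A reader might infer that Diamox is the reason the two tables differ and that one Diamox rule would make them comparable. Step 6 shows that it would not.

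**The documents do not reject these baselines.** This also stands. A reader might infer that the plan considers an IOP measured on Diamox unfit as a baseline, and so scores success on values it has discarded. The exclusion is stated without a reason, and it also covers thresholds that use no baseline.

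**The wider population may be deliberate.** Synopsis, protocol body and SAP agree, and scoring a composite in all eligible eyes is defensible. That is a good argument against making the restricted set the main table, which would depart from Protocol 14.2.5.2. It is no argument against showing the restricted result as well.

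**SAP 4.4.1 may inherit the rule from 4.4.** This is weak. The first paragraph of 4.4.1 restates the exclusion and the second names its own population. The protocol handles change and success in separate subsections. It is fair, though, that the eyes are kept by silence rather than by an explicit statement.

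**Oral drugs are reported.** SAP 4.3 describes oral IOP-lowering drugs by class at baseline and after implantation. That shows how common they are, but gives no success rate without those eyes.

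**Conclusion.** The inconsistency is real and appears in both documents: success is scored without the Diamox rule that governs the IOP-change, 20% and threshold results, unexplained and with no supportive analysis. It is one of two sources of non-comparability with the 20% table; the SSI and hypotony handling is the other and follows from the composite.

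A reader might infer that success will be understated. The documents do not support any direction. The range of -8 to +4 points rests wholly on the assumed shares and success rates, and the shift is zero if there are no Diamox eyes or if both groups succeed equally often. At shares of a few per cent it is well inside sampling error. The result is secondary and descriptive, so no power or error rate changes. This is a low-cost improvement, not a flaw that threatens the study's conclusions.

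**What to change.** Keep the protocol's population for qualified and complete success. Add to SAP 4.4.1 a row giving both success measures, at each time point, in eyes not on Diamox at the decision day, and print the denominators of both rows. Say in one sentence that the main success row includes baseline-Diamox eyes. A footnote should say that SSI eyes (and clinical-hypotony eyes, as the protocol has it) are outside the 20% table's denominator but count as failures in success, so that the remaining difference is not put down to Diamox.

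Diamox status on the decision day is already collected (Protocol 10.3), so no new data are needed. The cost is one extra row per success table and a smaller denominator in that row: at an assumed 10% share, 54 instead of 60 eyes.

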10.6.2 Best Corrected Visual Acuity

BCVA in the study eye will be collected at baseline and at all data collection points defined for the study. Values will be recorded in the eCRF according to local practice (Snellen, LogMAR, EDTRS, etc.) along with scale name or method used to assess BCVA.

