1.1. Background

The term “glaucoma” refers to a group of diseases that have in common a characteristic damage to the optic nerve with associated visual field loss. The goal in the treatment of glaucoma is to prevent further loss of functional vision and to avoid an adverse impact on the patient’s quality of life.¹ Currently, the only approach proven to be efficient in preserving visual function is lowering intra-ocular pressure (IOP)² as elevated IOP is recognised as the primary risk factor for glaucoma.

XEN 45 Gel Stent (Allergan Inc.) is an *ab interno* gelatin stent implanted via a clear corneal incision without conjunctival incision and is the only available filtering micro-invasive glaucoma surgery device that allows subconjunctival filtration. The XEN 45 Gel Stent is intended to reduce IOP in patients with primary open angle glaucoma where previous medical treatments have failed (XEN 45 Gel Stent directions for use). The performance and safety of XEN 45 Gel Stent has been previously demonstrated in a few clinical trials but the follow-up time has only been up to two years.

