 - Persistent corneal decompensation / edema (>30 days)
 - Mild corneal decompensation / edema

[figure not shown]

-
- Moderate corneal decompensation / edema
 - Severe corneal decompensation / edema
 - Cyclodialysis
 - Endophthalmitis
 - Hyphema
 - ≥ 2 mm in height (layered) at any time; present or arising > 30 days postoperatively
 - Persistent hypotony: IOP < 6 mmHg, present at two consecutive visits postoperatively > 30 days apart
 - Clinical hypotony: vision reduction (2 lines or more) related to macular changes consistent with hypotony maculopathy (macular folds), optic disc edema, and/or serious choroidal detachments because of low IOP
 - Implant blockage in the anterior chamber
 - Implant exposure or extrusion
 - Implant fracture
 - Implant migration
 - Implant repositioning requiring surgical intervention
 - Implant touching iris
 - Implant touching cornea
 - Iridodialysis
 - Iritis (requiring treatment after the postoperative medication taper)
 - Macular edema
 - Ptosis
 - Retinal detachment
 - Suture abscess or other local infection
 - Vitreous hemorrhage
 - Any other adverse event that leads to permanent visual impairment or requires surgical or medical intervention to prevent permanent visual impairment

2. Sample Size

A sample size of 150 patient eyes was selected, as it is anticipated that this will allow for the inclusion of a minimum of 60 independent study eyes have at least 3 years of follow-up data without a SSI for glaucoma after the initial implant with XEN 45 Gel Stent. Based on the Allergan study MS-001, for month 36 the 95% confidence interval (CI) of the projected mean IOP reduction afforded by a sample of 60 study eyes is -7.2 to -4.0 mmHg. That is, the half-length of the interval is 1.6 mmHg, which provides a reasonable precision for the estimate of the projected mean reduction in IOP.

3. Data Handling

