4.3. Disease progression

Ocular medical history will be summarised descriptively in the Safety Population overall and not by the time windows specified. Needling procedures will be summarized in the Safety Population by the time windows indicated in Section 4.1. Anti-metabolite/anti-fibrotic use will be described during the stent implantation, during conjunctiva bleb revision (if applicable), during needling procedures (if applicable), and also when used alone. Anti-metabolite/anti-fibrotic use during needling procedures will be determined based on the date of each anti-metabolite/anti-fibrotic use and date of the needling procedure; the same date assumes that the anti-metabolite/anti-fibrotic was used in conjunction with the needling procedure. IOP lowering medications (oral) will be described at baseline and post-implantation in the Effectiveness Population by class of medication (carbonic anhydrase inhibitors or alpha-agonist hypotensive agent). Visual field exam will be summarised descriptively at baseline and for all time points of interest (as described in Section 4.1) in the Safety Population. All BCVA values will be converted to logarithm of the minimum angle of resolution (logMAR) units.³ To do this, Snellen values will be converted by taking the negative base 10 logarithm of the decimal. ETDRS letters will be converted to approximate Snellen scores by the following formula.

$$\text{Snellen} \cong \exp \left\{ \frac{1}{50} (\text{ETDRS} - 85) \right\}.$$

This will then be converted into logMAR units using the negative base 10 logarithm of the decimal as above. Any non-numerical BCVA values (i.e. including count fingers, hand movement, light perception and non-light perception) will also be converted to logMAR units as described below:⁴

Non-numerical BCVA value	LogMAR
Count fingers (CF)	1.8
Hand movement (HM)	2.3

Light perception (LP)	2.8
No light perception (NLP)	3.0

4.4. Change in IOP and number of topical IOP-lowering medications after XEN 45 gel stent implantation

Change in IOP from medicated baseline and change in the number of topical IOP-lowering medications will be summarised. Change in number of IOP-lowering medications will be made by examining the class of the medication as follows:

- Beta Blocking Agents
- Carbonic Anhydrase Inhibitors
- Parasympathomimetics
- Prostaglandin Analogues
- Sympathomimetics In Glaucoma Therapy

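### An eye that loses light perception from a cause other than low IOP still counts as a qualified or complete success if it meets the remaining success conditions

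*SAP*

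**What the plan says.** Protocol 6.2 and SAP 1.4 define success identically. Complete success needs a fall in IOP of at least 20% from the medicated baseline, with "no SSI for glaucoma and no clinical hypotony while taking no topical IOP-lowering medications". Qualified success differs only in the drug condition: the eye may be on as many topical drugs as at baseline, or fewer.

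The one visual element is inside clinical hypotony, which SAP 1.8 describes as "Clinical hypotony: vision reduction (2 lines or more) related to macular changes consistent with hypotony maculopathy", or to disc oedema or choroidal detachment, in each case attributed to low IOP.

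SAP 4.4.1 then tabulates "The number and proportion of eyes achieving qualified or complete success at each time point of interest" (12, 24, 36, 48 and beyond 51 months) in the Effectiveness Population, and adds no further visual condition.

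The plan does provide for recording severe visual loss. Protocol 10.6.2 says "BCVA in the study eye will be collected at baseline and at all data collection points defined for the study". SAP 4.3 says "Any non-numerical BCVA values (i.e. including count fingers, hand movement, light perception and non-light perception) will also be converted to logMAR units", with light perception set at 2.8 and NLP at 3.0. The adverse events of special interest (AESIs) include endophthalmitis, retinal detachment and a catch-all for events causing permanent visual impairment. BCVA goes to a descriptive summary (Protocol 14.2.3) and AESIs to frequency tables (Protocol 14.2.5.3, SAP 4.5). Nothing carries either into success.

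**The concern.** The definition treats visual harm unevenly. A two-line loss caused by low IOP makes the eye a failure. Complete loss of light perception from endophthalmitis, retinal detachment or any other cause does not. By including clinical hypotony, the plan already accepts that some visual harm defeats success, yet it gives no reason for failing the smaller loss and passing the larger one.

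At stake is the meaning of a secondary endpoint. The same eye could appear as a serious harm in the safety tables and in the best category of the performance tables, with nothing to connect the two. If such an eye turns up, reclassifying it after the results are seen would be a post hoc choice. The data are anonymised and no queries can be sent to sites (Protocol 12 and 14.3.3), so the case could not be clarified later.

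**Working it through.** **The plan's own figure.** The only precision calculation is for mean IOP change (Protocol 14.1): mean −5.6 mmHg, SD 6.32, n = 60. The half-length is 1.96 × 6.32/√60 = 1.60, giving −7.2 to −4.0 mmHg, as stated. No precision is given for a success proportion.

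**Applying the written definition.** The definition is a true/false rule. The IOP values below are assumed for illustration.

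| Eye | IOP (mmHg) | Drops | Complete | Qualified |
|---|---|---|---|---|
| NLP, not from low IOP; no SSI | 20 to 14 (−30%) | 3 to 0 | Yes | Yes |
| Same, drops unchanged | 20 to 14 (−30%) | 3 to 3 | No | Yes |
| Same, smaller IOP fall | 20 to 18 (−10%) | 3 to 0 | No | No |
| NLP with clinical hypotony | 20 to 4 (−80%) | 3 to 0 | No | No |
| NLP and an SSI for glaucoma | 20 to 14 (−30%) | 3 to 0 | No | No |

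The first two rows show the gap. The last three show its limits: every other success condition must still be met.

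**Does other text close it?**
- Loss of vision is not an SSI (Protocol 10.8). It therefore does not end data collection, and the eye can still have a visit in the Month 33 to 39 window.
- The lower bound of 6 mmHg in SAP 4.4.1 belongs to the IOP-range counts, not to qualified or complete success.
- The BCVA and AESI summaries are separate tables.

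**Size.** One eye moves the proportion by 1/n.
- n = 60, the planned minimum with three years of follow-up and no SSI: 1/60 = 1.7 percentage points.
- n = 150, the planned selection, as an upper bound on the denominator: 1/150 = 0.7 points.

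The documents contain no rate of NLP. Taking 0 to 3 such eyes in 60 and 24/60 = 40.0% successes (both assumptions), counting them as failures gives 40.0%, 38.3%, 36.7% or 35.0%. For comparison, the 95% half-width at 40% is 1.96 × √(0.4 × 0.6/60) = 12.4 points.

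**Timing.** Under SAP 4.1, IOP and drug counts use Months 33 to 39. BCVA falls into groups of >24 to ≤36 and >36 to ≤48 months. The BCVA group therefore cannot show whether NLP came before the IOP visit. The BCVA date can.

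**The case against.** The best defence is that this is a choice of endpoint. Success is listed under performance outcomes and AESIs under safety outcomes, consistently in both documents. The device is intended to lower IOP, so an IOP-based composite is natural, and visual harm is reported elsewhere. That explains an IOP-centred endpoint. It does not explain why one visual harm fails the eye and a worse one passes.

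Two stronger readings are tempting and should be resisted.
- A reader might infer that the definition contradicts the plan's own aim, since SAP 1.1 says "The goal in the treatment of glaucoma is to prevent further loss of functional vision". That sentence is general background, and the next one presents IOP lowering as the only approach shown to preserve visual function. An IOP-based endpoint follows from that text.
- A reader might infer that losing light perception and stopping drops is enough to score as complete success, perhaps because drops are withdrawn once there is no vision left to protect. The IOP, SSI and hypotony conditions still apply, and the documents say nothing of such a motive.

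Three practical objections stand. The effect is small against sampling error. BCVA is outside the minimum required dataset (Protocol 8.2.3, SAP 1.7), so some losses will go unseen. An NLP criterion is also narrow: an eye reduced to hand movement or light perception would still pass, while NLP from an unrelated disease would fail. NLP is used because it is an unambiguous category already coded in the SAP; the point made here goes no further than that.

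**Conclusion.** The point holds as a limited gap in the success definition. An eye with new NLP not due to low IOP, and meeting all the other conditions, is scored as a success under Protocol 6.2, SAP 1.4 and SAP 4.4.1. The misclassification can only raise the success proportion.

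Its size cannot be estimated from the documents. It is 1.7 points per eye at 60 eyes and 0.7 at 150, and it may be nil. A reader might infer that the success rates are materially inflated; without a rate of NLP among eyes that meet the other conditions, the documents do not support that. The primary analysis of change in IOP and drug count, and the sample size, are untouched. This is a cheap improvement, worth making before the data are analysed.

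**What to change.** In SAP 1.4 and 4.4.1, with a note that this departs from Protocol 6.2, add a rule on these lines: an eye with NLP recorded on any date up to and including the IOP visit used for a time point, and not NLP at baseline, is not a qualified or complete success at that time point or later.

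Also specify:
- the comparison uses the BCVA date, not the BCVA time group;
- an eye without BCVA keeps its classification under the present definition, and the number of such eyes is reported;
- success is presented both with and without the rule, with the number of eyes reclassified.

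The cost is a short paragraph, one derivation from data already planned for collection, and one extra set of rows in the success table. The downsides are a possibly slightly lower success rate and a result that depends on BCVA being in the chart. Showing both versions keeps the protocol-defined result visible.
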